The three co-primary endpoints for this study are:

- a. ASES score at 22+ Months
- b. No unanticipated device-related adverse event, and no fracture, perforation of the bone or joint dislocation, and no fracture, perforation or dissociation of the device, and no revision or removal of any component, and
- c. Radiographic Success, as defined by:
 - a. Subsidence of the humeral component < 5 mm, and
 - b. Migration of the humeral component < 5mm, and
 - c. No progressive lucency around the humeral component >2mm in two or more contiguous zones
 - d. Migration of the glenoid component <5 mm, and
 - e. No progressive lucency >2mm around the entire glenoid component

SECONDARY ENDPOINTS

The data collected will also be analyzed for the following secondary endpoints:

- 1. American Shoulder and Elbow Surgeon's Score (ASES) at all time points
- 2. Single Assessment Numeric Evaluation (SANE) Score at all time points
- 3. Constant Score at all time points, except 6 weeks (adjusted for age and gender)
- 4. Radiographic assessment of radiolucencies and subsidence
- 5. Overall adverse events including removal/revision and other serious adverse events

The safety of the system will be monitored by recording adverse events including serious adverse events not considered UADEs throughout the follow-up period. Types of events to be collected include but are not limited to:

- Device removal or revisions
- Unanticipated adverse device events
- Systemic adverse events
- Local adverse events
- Reoperations and Other Interventions

Study participants will only be considered discontinued/withdrawn for the following reasons:

- Death
- Withdrawal of consent (written)
- Revision/Removal

Information from any patient who fails to return for multiple, consecutive, scheduled follow-up visits for any reason other than the criteria listed above will be identified as Missing Data.

ANTICIPATED CHANGES

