Information on plausible values of the percentage of patients projected to be radiographic failures was found by looking in the literature to find plausible rates for each component of the radiographic failure definition. Subsidence and migration of the humeral component and progressive radiolucency around the humeral component have been reported at approximately 2% and 0%, respectively. Migration of the glenoid component and progressive lucency of the glenoid component have been reported at approximately 5% and 6%, respectively⁶. Because some overlap is to be expected, the overall Radiographic Success rate is estimated to be 93% for sample size calculation purposes.

Assumptions:

α = 0.05	Probability of Type I error
β = 0.10	Probability of Type II error: power = $1 - \beta$
$p_{C} = p_{I} = 0.93$	Estimated success rate for Control and Investigational groups
δ = 0.10	Non-inferiority Margin

⁶ Sperling,et al. "Radiographic assessment of ingrowth total shoulder arthroplasty." *JBJS.* November/December 2000, Vol 9 No. 6, p 507-513.

Resulting sample sizes (number of shoulders), not adjusted for attrition, are 112 Investigational vs. 112 Control (5% type I error rate, 90% power). The sample size was increased by 15% to allow for possible attrition. This gives a sample size of 264 total subjects (132 Investigational and 132 Control).

Absence of Revision/Removal/UADE

Non-inferiority sample size calculations were implemented in nQuery Advisor 7.0 software using a 1:1 ratio of Investigational to Control subjects. This software uses methodology as described in a text by Farrington and Manning⁷.

The sample size needed to obtain 90% power for testing for non-inferiority of the investigational device to the control device with regard to Absence of Revision/Removal/UADE was calculated as follows:

Definitions:

p_I : Proportion of shoulders in the Investigational treatment group without a

Revision/Removal/UADE

 p_C : Proportion of shoulders the Control treatment group without a Revision/Removal/UADE δ : Non-inferiority margin. Lower 95% confidence bound for difference in proportions of clinically successful subjects at 22+ months (Investigational – Control) must be greater than $-\delta$.

For a specified constant, $0 < \delta < 1$, the hypotheses of non-inferiority are:

$$H_0: p_I - p_C \le -\delta vs. \quad H_A: p_I - p_C > -\delta.$$

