The relationship between radiographic images and clinical outcomes will be evaluated by investigating how the primary clinical outcome, which is the change in ASES score from baseline to 22+ months, is affected by the primary radiographic outcomes, specifically the absence/presence of migration, the absence/presence of subsidence, radiolucencies, and osteolysis. This will be done using two-sample t-tests to compare the average change from baseline for patients with and without migration, and for patients with and without subsidence.

A comparison of the rate of reoperation for investigational vs control will be made using a Fisher's exact test.

SAFETY EVALUATIONS

ADVERSE EVENTS

All adverse events will be recorded, described, and compared for Investigational and Control groups. Adverse events resulting in device removal and/or revision will be collected and evaluated for differences across the control and investigational populations. Frequencies of adverse events, revisions/removals, and device related adverse events will be compared for investigational and control groups using the Likelihood Ratio chi-square test.

DATA COLLECTION, HANDLING AND RETENTION SOURCE DOCUMENTATION REQUIREMENTS

Source documentation for this study will be maintained to document the treatment and study course of a subject and to substantiate the integrity of the trial data submitted for review to the regulatory agencies. Source documentation will include, but not be limited to, the paper or eCRF if data is directly entered there, study worksheets, hospital and/or clinic or office records documenting subject visits including study and other treatments or procedures, medical history and physical examination information, laboratory and special assessments results, device accountability records, and medical consultations. The investigator will make such records available for inspection by representatives of the sponsor, the IRB and the FDA, upon request.

CASE REPORT FORMS

Data for this clinical trial will be collected and documented on the subject Case Report Forms (CRFs) provided which may be in paper form or in an electronic form. Authorized study site personnel will complete CRFs only.

Sample CRFs to be used with this clinical trial are provided in Exhibit 4.

STUDY DOCUMENT RETENTION

Study documents must be retained for a minimum of two years following completion of the study or longer as required in 21CFR Part 812.140.

DATA REPORTING

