POTENTIAL RISKS ASSOCIATED WITH COMPREHENSIVE® SHOULDER SYSTEM WITH NANO HUMERAL COMPONENT IN TOTAL SHOULDER REPLACEMENT

The safety and efficacy of the Comprehensive[®] Shoulder System with nano humeral component has not been demonstrated clinically, and patients participating in the study may be subject to increased risks and/or adverse events, in addition to those listed under general surgical risks, including, but not limited to:

• Failure of biologic fixation resulting in loosening or migration of the implant

Risks/Benefits from the Investigational Device

All of the risks associated with the use of the nano humeral component are the same as those described for a total shoulder replacement arthroplasty. Given the stemless design of the nano humeral component, there may be an increased level in some of the implant-related risks, particularly for failure of biologic fixation resulting in loosening or migration of the implant. Loosening or migration could affect the implant position resulting in an unsatisfactory surgical outcome. Additional surgery would be required to replace the implant with an alternate prosthesis if excessive loosening or migration of the nano humeral component occurs.

Use of the nano humeral component prosthesis may benefit patients by reducing the amount of bone removed during the surgical procedure. In addition the nano humeral component does not violate the canal of the humerus. The amount of retained native bone is greater than for stemmed shoulder prostheses and could facilitate surgery for replacement of the nano humeral component with a micro or mini stem. Traditionally if a standard sized stem needs to be revised or removed, a "long" stem is used to replace it which results in a further violation of the canal and removal of bone. Leaving the canal intact allows the shaft of the humerus greater flexibility in adjusting to forces applied to it.

MINIMIZATION OF RISK

With the increased understanding of failure modes for total shoulders, pre-clinical testing and clinical results found in the literature, it is believed that none of the previously mentioned adverse events will occur in significantly higher numbers compared to the control device. This investigational plan has reduced the potential risk to the patient through the following methods:

- 1. By defining a patient population that limits the exposure of the device to patients conforming to the proposed indications, exclusions, and age requirements

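### The exploratory link between implant movement and ASES change rests on unadjusted present/absent t-tests with an undefined cut, and at the plan's own movement rates it is too imprecise to say much

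*Combined protocol and SAP*

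**What the plan says.** The final part of Exploratory Analyses (Statistical Analysis Plan, Efficacy Evaluations) sets out to relate the change in ASES from baseline to 22+ months to the radiographic findings, "specifically the absence/presence of migration, the absence/presence of subsidence, radiolucencies, and osteolysis". The method is two-sample t-tests on mean change, one for migration and one for subsidence: "This will be done using two-sample t-tests to compare the average change from baseline for patients with and without migration, and for patients with and" (the sentence then names subsidence). No method is given for radiolucencies or osteolysis.

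Other parts of the plan bear on this:

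- **Co-Primary Endpoints, Radiographic Success.** Movement is judged against 5 mm limits. The first criterion reads "Subsidence of the humeral component < 5 mm, and", and there is a matching limit for the other component: "Migration of the glenoid component <5 mm, and".
- **Sample Size Calculation, Radiographic Success.** The expected rates are "Subsidence and migration of the humeral component and progressive radiolucency around the humeral component have been reported at approximately 2% and 0%, respectively" and, for the glenoid, "Migration of the glenoid component and progressive lucency of the glenoid component have been reported at approximately 5% and 6%, respectively".
- **Section C, Risks/Benefits from the Investigational Device.** Loosening or migration is the risk that the stemless design may raise: "Loosening or migration could affect the implant position resulting in an unsatisfactory surgical outcome".
- **Significance Levels and footnote 14.** Exploratory results use a 5% level, are reported without claims of statistical significance, and are produced only where the data permit.

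**The concern.** Of the analyses the plan names, this is the only one that relates implant movement to how the patient fares. The regression models earlier in the same section list treatment group, age, gender, BMI, diagnosis and pre-operative ASES, but not movement.

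A present/absent split of a rare finding leaves one very small group and discards any gradation of movement in the others. The t-tests also leave out treatment group and pre-operative ASES, although both are covariates in those neighbouring models. Because neither component nor cut is stated, the size of the small group, and so the precision of the result, is unknown before the data are read.

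What is at stake is interpretation. A wide, inconclusive comparison tells the reader little about whether movement harms the patient, which matters for a stemless implant whose own risk section singles out migration.

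**Working it through.** **Inputs.** Evaluable shoulders: 224 (112 per arm). Enrolled: 264. Movement rates: about 2% humeral, about 5% glenoid (Sample Size Calculation, Radiographic Success). Difference: 9.5 points, borrowed from the ASES non-inferiority margin. SD: 19, the plan's post-operative SD; no SD of change is given, so using it for change is an assumption. Two-sided 5%: the plan gives the level but not the sidedness.

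**Reproducing the plan's figures.** The plan states no power for this analysis, so the check starts from its sample sizes.

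- ASES: n = 2 × (1.645 + 1.282)² × (19/9.5)² ≈ 69 per arm by the normal formula. The t-based version gives 70 (power 0.903), as stated.
- Radiographic Success: n = (1.645 + 1.282)² × 2 × 0.93 × 0.07 / 0.10² ≈ 112 per arm, and 112/0.85 ≈ 132, as stated.

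**Size of the small group.**

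- 2%: 0.02 × 224 = 4.5; 0.02 × 264 = 5.3.
- 5%: 0.05 × 224 = 11.2; 0.05 × 264 = 13.2.
- 7% (both components, no overlap): 0.07 × 224 = 15.7; 0.07 × 264 = 18.5.

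**Power and precision.** With k shoulders showing movement and m without, SE = 19 × √(1/k + 1/m). The noncentrality is 9.5/SE, and power comes from the noncentral t on k + m − 2 degrees of freedom. For 4 v 220, SE = 19 × √(0.25 + 0.00455) = 9.59 and the noncentrality is 0.991. The 95% half-width is 1.97 × SE.

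| With v without | Rate | Power | 95% half-width (points) |
|---|---|---|---|
| 4 v 220 | 2% | 16.7% | 18.9 |
| 5 v 219 | 2% | 19.6% | 16.9 |
| 5 v 259 | 2% | 19.7% | 16.9 |
| 6 v 258 | 2% | 22.6% | 15.4 |
| 11 v 213 | 5% | 36% | 11.6 |
| 13 v 251 | 5% | 42% | 10.6 |
| 15 v 209 | 7% | 46% | 10.0 |
| 19 v 245 | 7% | 55% | 8.9 |

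At 2%, averaging over the binomial count gives 18.0% for 224 shoulders and 20.4% for 264. The difference detectable with 80% power is about 24 to 27 points for 4 to 5 v about 220. Reaching 80% power at 9.5 points would take about 39 of 224 shoulders (17%) with movement.

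**Sensitivity at 4 to 5 v about 220.**

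- SD 15: 24–29%. SD 17: 20–23%. SD 22: 14–16%. SD 25: 12–13%.
- One-sided 5%: 26–29%.
- Welch's test: about 12–14%.
- If the 2% is shared between subsidence and migration, so that each test has 2 to 3 cases: 11–14%.
- With 224 shoulders, the chance of fewer than two cases is 0.060 at 2% and 0.343 at 1%.

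**What a millimetre regression might add.** The documents give no distribution of movement, so any figure rests on an assumed shape. With a linear relation scaled to give 9.5 points across an upper-2% cut, simulated power was 86% for normal, 46% for exponential and 37% for log-normal movement. It was 83%, 37% and 27% once reading error was added. A separate check with exponential movement gave about 45%, falling to 22% if nine in ten shoulders show no movement. If harm arises only above a sharp threshold, the regression does worse: 6–10% against about 18% for the t-test.

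**The case against.** Several points on the other side stand.

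- **The 2% is not the only relevant rate.** A reader might infer that this analysis has under 20% power across the board at the plan's own rate. The documents do not support that. The 2% is humeral only, the analysis names no component, and the 5% glenoid rate roughly doubles the power. Even for the humeral component, 20% is passed with six cases or a one-sided test, and is reached or passed with an SD of change of 17.
- **The cut is unstated.** The 2% was taken for the radiographic failure definition. If any detectable movement counts as present, the group could be much larger and the loss from splitting much smaller: about 4 to 11 percentage points of power in simulations with 25–50% prevalence.
- **The plan limits the claim.** It makes no significance claim for exploratory results and runs them only if the data allow. Nothing here touches the co-primary tests.
- **Adjustment is partly present.** Using change from baseline already takes some account of the pre-operative score.
- **Millimetre values may not exist.** The 5 mm limits suggest that movement is measured, but a reader could simply classify above or below 5 mm. Exhibit 3 and the case report forms are not available here.
- **A slope is not always better.** Section C speaks of excessive loosening or migration, which is compatible with a threshold effect.

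What survives is that every scenario built on the plan's own rates falls well short of 80% power, with intervals of about ±9 to ±19 points. Exploratory status is itself a reason to prefer estimates with intervals to sparse t-tests.

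**Conclusion.** The concern holds as an optional improvement to an exploratory analysis. As written, the analysis is unadjusted, leaves its split undefined, and is weak at the rates the plan expects: roughly 17–20% power for 9.5 points on the humeral rate, 36–42% on the glenoid rate, and 46–55% with both combined without overlap. These figures assume an SD of change of 19, two-sided 5% testing and 224 to 264 shoulders; the humeral range is for about 224.

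Two further inferences would go too far. One is that regression on millimetres would recover a large, known amount of power; without a distribution of movement that cannot be established, and under a threshold effect it could lose power. The other is that the weakness threatens study success or would lead the sponsor to declare movement harmless; the plan's rules on exploratory reporting do not support that reading.

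One feature could thin the group further. Patients whose humeral stem is removed leave follow-up (Discontinuations and Revisions), and a pre-revision ASES is collected only where feasible (Missing Data and Sensitivity Analyses). Some shoulders with the greatest movement may therefore have no 22+ month score.

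**What to change.** Amend the last part of Exploratory Analyses as follows:

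1. State which component (humeral, glenoid or both) and which millimetre cut define migration and subsidence as present.
2. Add a linear regression of 22+ month ASES on migration and subsidence, with treatment group and pre-operative ASES as covariates. Use millimetres where the central reader records them, and the present/absent indicator otherwise. With pre-operative ASES in the model, the movement coefficient is the same whether the outcome is the 22+ month score or the change.
3. Report each estimate with a 95% confidence interval.
4. Keep the with/without comparison beside it, showing the number of shoulders in each group.

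The cost is a few sentences in the plan and one more exploratory model. If millimetre readings are recorded, no new data are needed; Exhibit 3 should be checked for this. The downside is that a slope assumes a roughly linear relation and would be less sensitive than the with/without comparison if harm occurs only above a threshold, which is why both should be reported.

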The Comprehensive® Shoulder System with nano humeral component addresses these issues by offering a minimally invasive humeral component that allows the surgeon to recreate the patient's natural humeral head version and inclination, while also allowing unobstructed access to the glenoid. The Comprehensive® Shoulder System with nano humeral component is an evolved design based on the Biomet TESS® shoulder that is currently marketed outside of the United States including Europe and Canada. The Comprehensive® Shoulder System with nano humeral component has a reverse morse taper locking mechanism that allows it to interface with Biomet's current offering of Comprehensive® shoulder components for enhanced flexibility in the surgical suite. The Comprehensive® nano also utilizes Biomet's proven PPS® Porous Plasma Spray technology for proximal fixation.

SECTION A: PURPOSE PURPOSE/OBJECTIVES

The purpose of this clinical investigation is to establish the safety and efficacy of the Comprehensive® Shoulder System with nano humeral component in Total Shoulder Arthroplasty. Safety and efficacy of the device will be measured by collection and analysis of the following data at the two-year or greater time point (22 months post-operative or longer):

- 1. American Shoulder and Elbow Surgeons (ASES) Score
- 2. Single Assessment Numeric Evaluation (SANE)
- 3. Constant Score
- 4. Radiographic assessment of osteolysis, radiolucencies, migration, and subsidence
- 5. Comparison of overall adverse event rates including rates of removal/revision and other serious adverse events.

Please refer to the Statistical Analysis Section for a description of the analyses that will be used.

RATIONALE FOR CURRENT STUDY

The current study is designed to determine the safety and efficacy of the Comprehensive[®] Shoulder System with nano humeral component implants (investigational) by measuring clinical, radiographic and safety outcomes when compared to the Comprehensive[®] Shoulder System with mini stem component (control) at the two-year or later follow-up time point.

The data collected as part of this study will be used to support Pre-Market Notification (U.S.) clearance of the Comprehensive[®] nano Humeral shoulder system and as such will be conducted according to all relevant FDA regulations for IDE clinical trials, sponsor and IRB requirements.

SECTION B: PROTOCOL OVERALL DESIGN

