The study is designed as a prospective, multi-center, randomized, single blinded, controlled study. Patients will be enrolled at a maximum of seventeen (17) centers. Patients will be evaluated pre-operatively and at 6 weeks, 3 months, 1 year, 2 years and annually thereafter until the last patient entered into this study has completed their 2-year evaluation.

STUDY GROUPS AND TREATMENTS

Patients will be randomized to either the Comprehensive® Shoulder System with nano humeral component (investigational) or the Comprehensive® Shoulder System with mini stem component (control) group. Patients will be randomized using a 1:1 (Investigational: Control) blocked randomization plan. The treatment assignment will be revealed intraoperatively. Every attempt will be made to blind patients to their treatment until the end of the study. If a patient is revised or withdraws consent and at the request of the patient, blinding may be discontinued as no further data will be collected.

NUMBER OF PROCEDURES

A total of 264 subjects will be enrolled in this study (132 Control and 132 Investigational).

SELECTION OF SUBJECTS

All subjects considered for participation in the study will be assessed according to predetermined eligibility criteria, listed below. All subjects considered for enrollment must be

recorded on the Subject Screening Log (see Exhibit 11), including patients who are considered but not consented, consented but not randomized and consented and randomized.

Inclusion Criteria

- Patients with non-inflammatory degenerative joint disease including osteoarthritis.
- Patients where the device will be used in the correction of a functional deformity, specifically deformities that prevent congruent articulation of the glenohumeral joint. Examples include but are not limited to: humeral head structural deformity, osteophyte formation restricting range of motion, etc.
- Patients with pain and/or loss of function in the shoulder for whom other treatment modalities have been unsuccessful. Examples include but are not limited to: activity modification, physiotherapy, and anti-inflammatory or other types of medication.
- Patients requiring unilateral or staged bilateral shoulder arthroplasty

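### Outside co-primary (b) and Radiographic Success, the remaining safety measures get only tests of difference, with no risk difference or confidence bound, so a doubling of an uncommon event would usually go undetected.

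*Combined protocol and SAP*

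**What the plan says.** Section A (Purpose/Objectives) lists among the measures of safety and efficacy: "Comparison of overall adverse event rates including rates of removal/revision and other serious adverse events". The same items return as the fifth secondary endpoint.

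The analyses given for them are:

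- **Safety Evaluations, Adverse Events.** AEs are recorded and described, and "Frequencies of adverse events, revisions/removals, and device related adverse events will be compared for investigational and control groups", using the likelihood-ratio chi-square test.
- **Exploratory Analyses.** "A comparison of the rate of reoperation for investigational vs control will be made using a Fisher's exact test".
- **Categorical Data Analyses.** Categorical safety outcomes go to Fisher's exact test for 2x2 tables and to the likelihood-ratio test for larger tables.
- **Significance Levels.** Safety comparisons use 0.05 without adjustment and are reported as exploratory, with no claim of significance. Sidedness is not stated.

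No section names a risk difference, confidence bound or acceptable excess for AEs, SAEs, device-related AEs or reoperation, and no analysis specific to SAEs is described.

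Other safety content is better served. Co-primary (b) covers UADE, revision or removal, bone fracture or perforation, dislocation, and fracture, perforation or dissociation of the device. Radiographic Success covers subsidence, migration and progressive lucency. Each has a 10% margin and a one-sided 95% bound. Time to revision also has Kaplan-Meier curves and a proportional hazards model.

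**The concern.** A test of difference answers whether an excess has been shown. A safety comparison needs to say how large an excess the data still allow. With uncommon events and about 130 shoulders per arm, non-significance is the likely result whether or not the nano component carries a real excess. A table of p-values cannot separate those two situations.

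Co-primary (b) does not close the gap. The protocol's definition of a UADE leaves out events listed in Section C, and that list includes infection, instability, persistent pain, damage to surrounding tissue and soft-tissue reoperation. A serious, device-related event of these kinds falls outside (b) unless it also leads to revision or removal or involves one of the fracture, perforation, dislocation or dissociation items. It is then assessed only by a test of difference.

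**Working it through.** **Inputs.** Enrolment: "A total of 264 subjects will be enrolled in this study (132 Control and 132 Investigational". The evaluable number comes from the radiographic calculation: "Resulting sample sizes (number of shoulders), not adjusted for attrition, are 112 Investigational vs. 112 Control (5% type I error rate, 90% power". An allowance of 15% for attrition is then added. The safety level is 0.05, taken as two-sided because the named tests are conventionally so. The documents give no AE, SAE, device-related or reoperation rate, so the control rates below are assumptions. The 2% and 5% figures do appear in the sample-size section, but they belong to revision (and bone fracture or perforation) and to the co-primary (b) composite.

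**Step 1: reproduce the plan's figure.** The plan states: "overall Radiographic Success rate is estimated to be 93% for sample size calculation purposes". With success 0.93 in both arms, margin 0.10, one-sided 0.05 and 90% power:

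n = (1.645 + 1.282)² × 2 × 0.93 × 0.07 / 0.10² = 111.5, so 112 per arm. Then 112 / 0.85 = 131.8, so 132 per arm. Both match.

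**Step 2: power of the planned tests, 5% against 10%, 132 per arm.** Normal approximation, with mean rate 0.075:

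- √(2 × 0.075 × 0.925) = 0.3725 and √(0.05 × 0.95 + 0.10 × 0.90) = 0.3708
- z = (0.05 × √132 − 1.96 × 0.3725) / 0.3708 = −0.42, so power is 33.7%

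The exact figures sum the product of two binomial distributions over all tables with p < 0.05. Probability of missing the doubling:

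| Control → investigational | LR, 132 | Fisher, 132 | LR, 112 | Fisher, 112 |
|---|---|---|---|---|
| 2% → 4% | 80% | 93% | 81% | 94% |
| 5% → 10% | 64% | 75% | 69% | 78% |
| 10% → 20% | 36% | 43% | 43% | 51% |

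For commoner events the problem fades. Likelihood-ratio power at 132 per arm is 84% for 15% against 30%, and 95% for 20% against 40%. If the safety tests were one-sided at 0.05, the miss rate for 5% against 10% would be about 54% (132 per arm) to 59% (112 per arm) by the normal approximation.

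**Step 3: size of the two tests.** Exact type I error at 132 per arm:

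| True rate, both arms | LR | Fisher |
|---|---|---|
| 2% | 9.0% | 0.9% |
| 5% | 6.0% | 2.2% |

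The likelihood-ratio test rejects too often for rare events, so part of its apparent power advantage is not real. The choice of test can also decide the result: 7 against 16 events out of 132 gives p = 0.047 by likelihood-ratio and p = 0.079 by Fisher.

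**Step 4: what a bound would show.** Take 7 control and 14 investigational events out of 132, an observed doubling. Neither test is significant.

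- Risk difference: 14/132 − 7/132 = 5.3 points
- Wald standard error: √(0.1061 × 0.8939/132 + 0.0530 × 0.9470/132) = 0.0331
- One-sided 95% upper bound: 5.3 + 1.645 × 3.31 = 10.8 points (Wald). Solving the score equation instead gives 11.1 points.

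The methods differ most when events are few: with 3 of 132 in each arm the upper bound is 3.6 points by score and 3.0 by Wald.

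**Step 5: would more patients be the answer?** Detecting 5% against 10%, two-sided, at 80% power needs (1.96 × 0.3725 + 0.842 × 0.3708)² / 0.05² ≈ 435 per arm; 90% power needs 582. That is far beyond this trial, so the practical remedy is to report the uncertainty.

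**The case against.** The strongest case against has four parts.

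1. **The main device hazard is bounded.** Section C singles out failure of fixation, with loosening or migration, as the risk the nano component may raise. Radiographic Success puts a 10% margin on subsidence, migration and lucency, and co-primary (b) does so for revision and the main mechanical failures. This stands. A reader might infer that safety as a whole, or everything outside (b), has no bound; the documents do not support that. Revision also has planned time-to-event estimates, although a footnote makes these conditional on the data.
2. **The 5% rate is not the plan's rate for these events.** This stands too. A reader might carry the headline figure over to overall AEs. Those are collected regardless of cause, in patients up to age 90, for at least two years, and may well exceed 5%. The figure applies to uncommon categories only.
3. **The plan limits inference.** Safety results are exploratory, and study success depends on the three co-primaries alone. A reader might infer that the plan will declare safety from a non-significant p-value. No section says so. In Minimization of Risk, the belief that "none of the previously mentioned adverse events will occur in significantly higher numbers compared to the control device" is a prospective risk statement tied to no test; it need not be reworded. The exploratory label still supplies no bound.
4. **AEs will be described, so a difference can be worked out from the arm frequencies.** Partly so. It needs counts of shoulders with at least one event, which are not specified, and a bound left to be chosen later is not a planned one.

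**Conclusion.** The concern holds within limits. For any AE, other SAEs, device-related non-UADE events and reoperation, the plan offers only tests of difference, while Section A makes the overall AE and other SAE comparison part of establishing safety. For an uncommon category, assumed at 5% in controls, the planned tests miss a doubling in 64% to 75% of trials at 132 per arm and in 69% to 78% at 112. From 2% they miss 80% to 93%, and from 10% they miss 36% to 43%, both at 132 per arm. These figures rest on assumed rates, two-sided 0.05 and independent shoulders. For common events a doubling would usually be detected.

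The two sections that name tests also disagree for 2x2 safety tables (Fisher in one, likelihood-ratio in the other), which moves power for 5% against 10% by about 10 points. The effect is on how the safety tables will be read. The primary analysis, the study-success rule and the sample size are unaffected. The change should be made because the better display costs almost nothing.

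**What to change.** In Safety Evaluations, and for reoperation in Exploratory Analyses:

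- For any AE, any SAE, device-related AE and reoperation, report per arm the number of shoulders with at least one event, the risk difference (Investigational minus Control) and its one-sided 95% upper bound by a score method.
- Keep p-values as descriptive, and state their sidedness.
- State that a non-significant difference will not be interpreted as equal safety.
- Reconcile Categorical Data Analyses with Safety Evaluations by naming one test for 2x2 tables, bearing in mind that the likelihood-ratio test is anti-conservative when events are rare.

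The cost is some SAP wording and one extra column per safety table, with no new data or patients. The downside is that the report will show openly that sizeable excesses of rare events cannot be excluded.
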